### 9.3.3 Additional exploratory analyses

Additional analyses will be performed to examine the empirical cumulative distribution function of the change from baseline at EOT for the ORCA t-score, CGI-I, CGI-S, ABC-2 total score, CSHQ total score, GIHQ total frequency score, the BPI-SF total score, each BPI-SF domain score, VABS-3 composite score, VABS-3 GSV scores, VABS-3 raw scores, QL-Disability overall score, and ICND score will be plotted.

Test-retest reliability will be assessed for assessments collected more than once during the Screening period (Visits 1, 2, and 3, pre-dosing) using ICC. A correlation analysis of the efficacy measures will be done using Pearson correlation coefficients. The correlation of each total or overall score and CGI-I and CGI-S domain scores at EOT will be measured against the others and presented in a table and a heat map/matrix.

Waterfall plots may also be created for each post-baseline visit with the plots crosshatched to indicate genotype, History of Regression (yes, no), ASD diagnosis (yes no), depending on the number of subjects in each subgroup.

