The underlying neuropathology and severe neurological and neurodevelopmental impairments also lead to neurobehavioral dysfunction and dysregulation which substantially disrupt daily activities, put individuals at greater risk of harm, and can be potentially life-threatening. Hyperventilation and apnea result in a number of negative impacts on health including swollen abdomen, excessive burping, decreased oxygen saturation, changes in pallor, cyanosis, chronic hypoxia, and finger clubbing.^{6,9,10} Seizures can be debilitating to cognitive and neurological development. Self-injurious behaviors put individuals with PTHS at risk of physical harm, potentially with long-term cumulative effects which decreases overall quality of life. There is currently no on-going natural history study of PTHS. Cohort studies, and a recent consensus statement paper on diagnosis and treatment³ have provided detailed information characterizing the clinical manifestations of the disorder and their functional impact. This has provided insights on the symptoms that are central to the disorder and are important to patient functioning and well-being. The Pitt Hopkins Research Foundation (PHRF) maintains a family registry as part of the Coordination of Rare Diseases (CoRDS) Registry at Sanford which collects information on clinical symptoms (https://pitthopkins.org/research/how-to-get-involved-in-research-today/family-registry/). The PHRF also did an assessment of the patient and family experience by conducting a trend analysis of data shared through social networks.³⁴ In this analysis they identified the most concerning symptoms, most common methods of disease management, and unmet needs.

Together, the output from these initiatives and expert clinical advice has provided guidance into the important domain areas to address with NNZ-2591 treatment that would be most relevant and potentially beneficial to patients with PTHS (see Section 9.5.9). The secondary outcome of efficacy in this study will be assessed by evaluating a range of symptom areas to determine if there is preliminary evidence of efficacy, but also importantly to gather information about the performance of outcome measures and the influence of baseline patient attributes on clinical response.

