9.5.9.2 Clinical Global Impression of Improvement (CGI-I)

Clinical Global Impression of Improvement assessments will be made at Visit 9 (Week 6), EOT (Week 13, Visit 16), and Follow-up (Week 15, Visit 17). The CGI-I scale³⁶ requires the Investigator to rate how much the participant's illness has improved or worsened relative to a baseline state. A 7-point scale is used with the following values: 1, very much improved; 2, much improved; 3, minimally improved; 4, no change; 5, minimally worse; 6, much worse; 7, very much worse. The CGI-I will be evaluated using PTHS-specific scoring anchors. The clinicians will provide an overall global improvement rating and an improvement rating for each of seven domains: language/communication, social initiation/social avoidance, fine motor functioning/self-help challenging behavior, ambulation/gross motor, gastrointestinal issues, and autonomic/breathing abnormalities. The clinician should assess the participant's current state taking into consideration observations at the visit and symptoms within the last week. The rating of change is compared with status at Baseline (Visit 3). To ensure that interpretation of the scoring rubric is normalized among the raters, clinicians administering the CGI-I will be required to complete scoring calibration training.

9.5.9.3 Bayley Scales of Infant Development v4 (BSID4) or Stanford-Binet Intelligence Scales v5 (SB5)

The Stanford-Binet Intelligence Scales version 5 (SB5) assessment will be done at Screening (Visit 1) and EOT (Week 13, Visit 16). SB5 is validated for ages 2 to 85+ and measures both verbal and nonverbal intellectual and cognitive abilities through a set of 10 subtests. The General cognitive ability is reported as a full-scale intellectual quotient score (FSIQ). Cognitive ability in five categories are reported in the index scores: fluid reasoning (FR), knowledge (KN), quantitative reasoning (QR), visual-spatial processing (VS), and working memory (WM). Non-verbal (NVIQ) and verbal intelligence quotients (VIQ) are also calculated. Scoring of index scores and IQ will be calculated using the z-deviation method for intellectual disability.

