### 5.3 Definitions

- Age will be derived as the integer value of (informed consent/assent date date of birth + 1)/365.25.
- The age at time of assessment will be derived as the integer value of (date of assessment date of birth + 1)/365.25.

- Body Mass Index (BMI) will be derived as weight in kilograms divided by height in meters squared.
- The change from Baseline measurement for a variable at a particular visit will be derived as the measurement taken at the specified visit minus the baseline measurement. For the Clinical Global Impression Scale Improvement and Caregiver Impression of Change, change from Baseline is the value at the visit.
- Treatment duration in days will be derived as follows: Date of Last Dose Date of First Dose + 1.
- The number of expected doses will be derived as (2\*treatment duration in days)-1, as subjects are expected to receive only their morning dose on the last day of treatment
- The number of doses taken will be derived as the number of doses taken as indicated by the Administration of First Dose CRF and by the Daily Dosing Log CRF for remaining doses, based on completed date and dose fields
- Number of missed doses will be derived based on the number of expected doses the number of doses taken
- Study Day will be derived as Date of Event Date of First Dose (+1 if the date of event ≥ date of first dose)
- Screening/baseline duration in days will be derived as follows: Date of First Dose Date of Screening
- Study duration will be defined as the total number of days in the study (date of last visit date of informed consent + 1).
- History of developmental regression will be determined from the PTHS diagnosis page of the CRF question: "Has the child undergone a regression of skills in the past?" If coded as "yes" the subject is considered as having had a past developmental regression.
- Autism Spectrum Disorder (ASD) diagnosis will be derived from the PTHS diagnosis page of the CRF. If ASD is checked under "confirmation of psychiatric co-morbidities", the subject is considered as having the disorder.
- Bipolar Disorder will be derived from the PTHS diagnosis page of the CRF. If "Bipolar disorders" is checked under "confirmation of psychiatric comorbidities", the subject is considered as having the disorder.

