A correlation analysis of the efficacy measures will be done using Pearson correlation coefficients at Baseline and EOT. The correlation of each total score will be measured against the others and presented in a table and a heat map/matrix. CGI-I and CGI-S domain scores will also be included in the correlation analysis. Test-retest reliability will be assessed for continuous efficacy assessments collected more than once during the Screening period (Visits 1, 2, and 3, pre-dosing) using Intraclass Correlation Coefficients

Statistical Analysis Plan 30APR2024

(ICC). The ICC will be based on covariance parameter estimates from a Restricted Maximum Likelihood Mixed Model including results from assessments conducted during the Screening/Baseline period with a random effect for subject. The ICC will be derived as: ICC = Within-subject covariance/Total covariance. ICC values range from 0 to 1, with values closer to 1 indicating greater test-retest reliability.

A treatment policy estimand will be used for all endpoints. The variables of interest are numeric scores associated with subject responses. Summaries will be performed on the observed data. There will be no imputations for completely missing scores or intercurrent events. Handling of missing responses items that contribute to total and subscale scores are defined in Section 5.2.5.

Results for each efficacy variable will also be listed by subject.

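### The planned correlation matrix pairs CGI-I, already a change rating, with the other scales' EOT level scores, which attenuates its correlation with scales whose change tracks it

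*SAP*

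**What the plan says.** SAP 9.2 (Secondary Efficacy Analysis) introduces the analysis: "A correlation analysis of the efficacy measures will be done using Pearson correlation coefficients at Baseline and EOT". It then fixes the pairs: "The correlation of each total score will be measured against the others and presented in a table and a heat map/matrix", and adds the CGI-I and CGI-S domain scores. SAP 9.3.3, as worded in Final Version 1.0, repeats the plan for EOT: "The correlation of each total or overall score and CGI-I and CGI-S domain scores at EOT will be measured against the others".

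Two features show that levels are meant. A Baseline matrix can contain only levels, and SAP 9.2 names Baseline and EOT together. SAP 9.3.3 also names change explicitly when it wants change, in the sentence on distribution functions: "Additional analyses will be performed to examine the empirical cumulative distribution function of the change from baseline at EOT". Its correlation sentence has no such words.

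CGI-I is not a level. SAP 5.3 says: "For the Clinical Global Impression Scale Improvement and Caregiver Impression of Change, change from Baseline is the value at the visit". Protocol 9.5.9.2 has the clinician rate against status at Visit 3, with the first rating at Week 6, so no Baseline CGI-I exists to enter a Baseline matrix.

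Protocol 6.2.2 gives the efficacy work a second purpose beyond preliminary evidence: to "gather information about the performance of outcome measures".

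**The concern.** At EOT the matrix correlates CGI-I (overall and domains) with the EOT levels of CGI-S, ABC-2, CSHQ, GIHQ, BPI-SF, ORCA, Vineland, QI-Disability and ICND. Caregiver Impression of Change, if its overall score is included, has the same mismatch against those levels.

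An EOT level is the baseline level plus the change. Where children differ widely and persistently, most of the spread in the EOT score is the difference they started with, which CGI-I is not meant to reflect. A scale whose change follows the clinician's rating closely can then show only a modest correlation in the table. Whether a scale moves with clinician-rated improvement is one part of how it performs as an outcome measure, and the matrix as written does not answer that.

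**Working it through.** The plan gives no figure for this matrix, so there is none to reproduce. The check is a closed-form attenuation calculation.

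**Inputs.** From the documents: CGI-I is a change (SAP 5.3); the matrix uses scores at EOT (SAP 9.2, 9.3.3); baseline is the average of pre-dose values where more than one was scheduled (SAP 5.2.4); ABC-2, CSHQ and GIHQ are each collected at Visits 1, 2 and 3 (SAP 9.2.9, 9.2.11, 9.2.12). Assumed, because the documents do not give them: the true change correlation r_d = 0.60, and rho from 0.5 to 0.9. The CGI-I standard deviation of 0.7 in the sample-size section cancels out of a correlation.

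**Notation.** B = baseline, E = EOT score, D = E − B, r_d = corr(CGI-I, D), rho = corr(B, E). Only sizes are shown; the sign depends on each scale's direction.

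**Equal variances, single baseline.** SD(D)/SD(E) = sqrt(2(1 − rho)) and corr(E, D) = sqrt((1 − rho)/2).

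- Case 1, CGI-I related to the scale only through its change: corr(CGI-I, E) = r_d × sqrt((1 − rho)/2).
- Case 2, CGI-I uncorrelated with baseline: cov(CGI-I, E) = cov(CGI-I, D), so corr(CGI-I, E) = r_d × sqrt(2(1 − rho)), exactly double case 1.

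**Baseline averaged over three visits** (equal single-visit variances, every pair of visits correlated rho). Var(B) = (1 + 2 rho)/3, so Var(D) = 1 + (1 + 2 rho)/3 − 2 rho = 4(1 − rho)/3, and cov(E, D) = 1 − rho.

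- Case 1: factor (1 − rho)/sqrt(4(1 − rho)/3) = sqrt(0.75(1 − rho)).
- Case 2: factor sqrt(4(1 − rho)/3).

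Factor, then the correlation the matrix would show for r_d = 0.60:

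| rho | Single, case 1 | Single, case 2 | Three-visit, case 1 | Three-visit, case 2 |
|---|---|---|---|---|
| 0.5 | 0.50 → 0.30 | 1.00 → 0.60 | 0.61 → 0.37 | 0.82 → 0.49 |
| 0.7 | 0.39 → 0.23 | 0.77 → 0.46 | 0.47 → 0.28 | 0.63 → 0.38 |
| 0.8 | 0.32 → 0.19 | 0.63 → 0.38 | 0.39 → 0.23 | 0.52 → 0.31 |
| 0.9 | 0.22 → 0.13 | 0.45 → 0.27 | 0.27 → 0.16 | 0.37 → 0.22 |

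For ABC-2, CSHQ and GIHQ, averaging the baseline raises the lower end and reduces the upper end.

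**CGI-S.** Entry requires a Screening score of at least 4, which narrows the spread between children. In a simulation with baseline CGI-S limited to 4–7 and assumed changes, CGI-I correlated 0.64 to 0.71 with change in CGI-S and 0.26 to 0.45 with its EOT level: attenuated, but well away from zero.

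**Precision.** With 10 to 20 children planned, every coefficient is imprecise. At N = 20, an observed 0.70 has an approximate 95% interval of 0.37 to 0.87; an observed 0.20 has −0.27 to 0.59.

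**The case against.** A reader might infer that a scale tracking CGI-I well will look almost unrelated to it. The documents do not support that as a general statement. They give no baseline-to-EOT correlation, and the smallest coefficients need both a high rho (about 0.9 or more) and the less favourable structure. If CGI-I is uncorrelated with baseline the factor doubles, and at rho 0.5 with a single baseline nothing is lost. This objection stands and sets the size of the claim.

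A reader might also infer that the matrix will decide endpoints for a later trial. No passage says so. The SAP places it beside the test-retest analysis, and a level-against-level correlation with CGI-S is an ordinary convergent-validity check. SAP Section 5 calls the tests descriptive, and no significance rule is attached to the matrix.

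Change is also examined elsewhere, by signed-rank tests, waterfall and forest plots, and distribution functions. Subject-level listings would let someone rebuild the CGI-I-against-change pairs. These limit the harm, but none of them is the missing correlation.

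Finally, the SAP addendum's contents list Section 9.3.3, and its revised wording is not in the text available to me, so the 9.3.3 sentence may have changed. The general text of Section 9.2 is not listed as updated and supports the same reading on its own. The absence of a CGI-I-against-change analysis can be asserted only for the text I could read.

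**Conclusion.** The mismatch is real: SAP 9.2, and 9.3.3 as worded in Version 1.0, correlate a change rating with EOT levels. The consequence is attenuation, severe for scales with stable differences between children and modest or absent at lower stability. The ranges in the working rest on an assumed change correlation of 0.60, an assumed rho and equal single-visit variances; they illustrate the effect and do not predict the trial's results. CGI-I against Caregiver Impression of Change is like with like and is not affected.

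Importance is low to moderate. The matrix is exploratory, and no efficacy test or sample size depends on it. As written, though, it cannot show which scales move with clinician-rated improvement, which is part of what the protocol says it wants to learn about the outcome measures.

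**What to change.** In SAP 9.2 and 9.3.3, state that CGI-I and Caregiver Impression of Change (overall and domain scores) will be correlated with the change from baseline to EOT in each other score. Keep the Baseline and EOT level matrices for level measures only, that is CGI-S and the scale totals. Spearman coefficients beside Pearson for the 7-point ratings are optional.

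The cost is a sentence in each section and one extra table or heat map. The change scores are already derived for the signed-rank tests, so no new data are needed. The change should be made before database lock, because SAP Section 5 treats analyses added later as exploratory and has post hoc ones labelled as such.

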# 10 Tables, Listings, and Figures

A list of the tables, listings, and figures will be maintained outside of this document and may be amended as needed.

Data listings will be sorted by subject number, then chronologically (if appropriate) as indicated by visit, date, and time. All data recorded on the CRFs will be included in the listings as appropriate as well as some derived information. Data on other treatments (e.g. behavioral treatments, supplements and special diets) were originally collected on three separate CRFs in the EDC: "Other Treatments", "Supplements and Complementary Treatments" and "Behavioral/Educational Treatments". Since the CRFs were duplicative the "Supplements and Complementary Treatments" and "Behavioral/Educational Treatments" and "Behavioral/Educational Treatments" were closed and only the "Other Treatments" CRF page was used. For the listing, the data from these three CRF pages will be combined and included in a single listing "Other Treatments." The "New Symptoms Log" was closed so the listing will only include data up until the time the log was closed in the EDC.

Listings of Subject Disposition, Protocol Deviations, and Inclusion/Exclusion Criteria Not Met will display results for All Subjects. Other listings will display results for the Safety or Intent to Treat Populations as appropriate.

Rounding for all variables will occur only as the last step, immediately prior to presentation in listings, tables, and figures. No intermediate rounding will be performed

on derived variables. The standard rounding practice of rounding numbers ending in 0-4 down and numbers ending in 5-9 up will be employed.

Tables will generally be presented with the parameter in the first column followed by the summary column(s). The presentation of numerical values will adhere to the following guidelines:

- Raw measurements will be reported to the number of significant digits as captured electronically or on the CRFs.
- Rounding:
  - For derived parameters or raw results with more than 2 decimals:
    - Standard deviations will be reported to four decimal places
    - Means and medians will be reported to three decimal places
    - Minimums and maximums will be reported to two decimal places
  - For other parameters:
    - Standard deviations will be reported to two decimal places beyond the number of decimal places the original parameter is presented.
    - Means and medians will be reported to one decimal place beyond the number of decimal places the original parameter is presented.
    - Minimums and maximums will be reported to the same number of significant digits as the parameter.
- Calculated percentages will be reported with no decimals.

P-values will be presented to four decimal places. If a p-value is less than 0.0001 then it will be presented as "<0.0001".

